Interestingly, it is unknown if the reduction in caries activity brought about the use of nanosilver fluoride is due to its remineralizing action, antibacterial action, or due to a combination of both.^{17,18} There is a need to understand the interaction of topical caries arresting agents like NSF and SDF with the oral microbiome associated with dental caries, since the in vitro findings cannot be extrapolated to the clinical use of NSF.¹⁹

To our knowledge, no publication has reported the in vivo antimicrobial efficiency of NSF on the primary dentition in comparison to SDF. Therefore, this study will be undertaken to evaluate and compare the clinical antibacterial and cariostatic effectiveness of NSF compared to that of SDF in 4-6 year old children. The null hypothesis of this study is that no statistically significant difference will be detected regarding the antibacterial effect of nanosilver fluoride in relation to caries activity in dentin caries lesions of primary teeth, in comparison to silver diamine fluoride, after one month.

AIM OF THE STUDY

General aim

To assess the antibacterial effect of nanosilver fluoride in relation to caries activity in dentin caries lesions of primary teeth in comparison to silver diamine fluoride after one month.

Specific aims

- To compare the change in *Streptococcus mutans* and *Lactobacilli* counts in dentin caries lesions of primary teeth after one month of the application of nanosilver fluoride or silver diamine fluoride.
- To compare the effect of nanosilver fluoride to that of silver diamine fluoride on caries lesion activity in dentin caries lesions of primary teeth after one month of application according to ICDAS criteria.

MATERIALS AND METHODS

Study Design

This will be a randomized, parallel, two-arm clinical trial, with a 1:1 allocation ratio. It will be set up and reported according to the CONSORT guidelines.²⁰

The PICOT question is: will children (4-6 years old) with an active carious lesion (ICDAS code 5) (population; P) using nanosilver fluoride varnish (Intervention; I) in comparison to silver diamine fluoride (comparison; C) show a greater percentage decrease in bacterial counts in the caries lesion (outcome; O) after 1 month follow-up (time; T)?

Study Setting and Location

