The study will take place in the Department of Pediatric Dentistry and Dental Public Health at the Faculty of Dentistry and the Department of Medical Microbiology and Immunology at the Faculty of Medicine, Alexandria University, Alexandria, Egypt.

Sample

Sample size estimation

The minimum sample size was calculated based on the results of a previous study.⁶ Adopting a power of 80% and a statistical significance level of 5% ($\alpha=0.05$), 24 children in each group will be needed to generate a statistically significant result. The sample size will be increased to 25 children of both genders per group to compensate for possible drop-out participants. Total sample size= $25 \times 2 = 50$. The sample size estimation was based on Rosner's method²¹ and calculated using G*Power 3.1.9.7.²²

Eligibility criteria

The participants enrolled in this study will be selected after fulfilling the following criteria:

Inclusion Criteria

- Children aged 4-6 years old.
- The presence of at least one active carious lesion on a primary tooth, with a score of 5 according to the International Detection and Assessment System (ICDAS), detected by visual-tactile inspection to assess lesion severity and activity.²³ (Appendix I, Tables 1 and 2)
- Completion of an informed consent to participate in the study.

Exclusion criteria

- Children reporting spontaneous or elicited pain from caries or showing any signs of pulpal infection, swelling, abscess, obvious discoloration of the tooth, or premature mobility.¹¹
- Reported usage of local or systemic antibiotics, chlorhexidine or fluoride mouthwashes within the last 2 weeks.²⁴
- Children presenting with special health care needs or undergoing medical treatment for chronic or acute diseases affecting salivary flow.
- Allergy or sensitivity to silver or any of the materials included in the study.¹¹
- Child weight less than 10 Kg (to avoid concerns for toxicity).²⁵

Randomization technique and allocation²⁶

Subjects complying with the inclusion criteria will be randomly assigned using a computer-generated list of random numbers to either the NSF or the SDF group (www.random.org). Allocation will be performed by a trial independent individual and the allocation ratio is intended to be equal (1:1).

Allocation concealment²⁷

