*** Himedia Laboratories, Mumbai, India.

****Red line by binder

Method

First visit: baseline examination

After obtaining the informed consent from the care giver/parent, the researcher will provide oral hygiene instructions to each of the study participants and will inform them about the importance of maintaining good oral hygiene and a proper diet.²⁹ The patients and caregivers will be informed about the therapeutic intervention to be applied, the possible outcomes, and side effects in detail. All of the examinations and interventions will be done by one calibrated examiner. All of the lesions in the children's oral cavity indicated for treatment with NSF or SDF will be treated and sampled for microbiological analysis.³⁰

On the day of the intervention, the children will be asked to refrain from tooth brushing in the morning, as well as eating and drinking (except water) for at least two hours before the appointment. The dmf index will be recorded for each patient.

For caries treatment in all groups, no caries or unsupported enamel will be removed. The patients will be instructed to rinse with a cup of water, then any gross debris will be gently removed with a piece of gauze. The tooth will then be partially isolated using cotton rolls and a saliva ejector. Additionally, petroleum jelly will be applied to the gingiva for added protection. Before applying the intervention, a 2-mm wide microbrush will be rubbed on the carious lesion for 4 seconds to collect the baseline microbiological sample.⁶ The microbrush will then be inserted in a sterile test tube containing 1 mL of saline and transported to the microbiology laboratory within 1-2 hours.³¹

Intervention

Test group (NSF):

- 1 drop of NSF will be dispensed into a sterile plastic dappen dish.

- Affected tooth surfaces will be dried with a gentle flow of air.
- The solution will be applied to the carious lesions using a microbrush.
- No more than one drop of NSF will be used for each patient.
- The NSF solution will be left in contact with the tooth surface for 1 minute.³²
- Any excess will be removed with a cotton pellet to minimize systemic absorption.

Control group (SDF):

It will be applied according to the manufacturer's instructions and the AAPD guidelines for using SDF.^{28,30}

- One drop of 38% SDF will be dispensed into a sterile plastic dappen dish.
- Affected tooth surfaces will be dried with a gentle flow of air.

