- A microbrush will be dipped into the SDF and dabbed on the side of the dappen dish to remove excess liquid before applying the solution to only the affected tooth surface.
- No more than one drop of SDF will be used for each patient.
- The SDF will be allowed to dry on the lesion for 1 minute.³³
- Any excess will be removed with a cotton pellet to minimize systemic absorption.

After the application of fluoride agents, all of the children will be instructed not to drink or eat for 1 hour after the appointment, their parents will be asked to observe this instruction.²⁴ Additionally, for ethical considerations, teeth not treated with SDF or NSF or those showing signs of failure or any new carious lesions that will appear during follow-up period will be appropriately treated.

Microbiological Procedure

1. Sample dilution

All samples will be dispersed by vortexing for 30 seconds then 10-fold serially diluted using sterile saline. A measure of the dilution will then be used for traditional plate culturing methods.^{34,35}

2. Culture

Aliquots of 10 ml of each dilution will be inoculated into freshly prepared Mitis Salivarius agar and Rogosa agar media respectively, using a micropipette.

- Mitis Salivarius agar plates will be incubated anaerobically in an atmosphere containing 10% CO₂ at 37°C for 72 hours to detect *Streptococcus mutans* counts.
- Rogosa agar plates will be incubated aerobically at 37° C for 48 hours to detect *Lactobacilli* count.

3. Isolation and Enumeration

Following the predetermined incubation period, colonies grown on the specified media will be counted and represented as (CFU/ml). *Streptococcus mutans* will be identified based on their characteristic morphology on Mitis Salivarius agar plates. Similarly, *Lactobacilli* will be identified biochemically and microscopically on the basis of their morphology.

4. Colony count

The number of colonies will be determined and expressed as colony forming units using the following equation.³⁶

$$\text{CFU/ml} = \frac{\text{n}^{\circ} \text{ of colonies} \times \text{dilution factor}}{\text{Volume taken in ml (1)}}$$

STUDY OUTCOME

Treatment effect will be evaluated after one month by comparing:

- Microbiological assessment of colony forming units (CFU) of *Streptococcus mutans* and *Lactobacilli*.
- Caries activity according to ICDAS criteria.

Follow up

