All patients will be recalled after one month. On the day of the recall appointment, patient preparation will be done as mentioned before.

Outcome assessment

- Microbiological assessment will be done as mentioned before and CFU counts will be recorded.
- Lesion activity will be assessed according to the ICDAS criteria. Using a blunt ended probe, if the cavity is found to be shiny and feels hard on gentle probing of the dentin, it will be recorded as an inactive lesion. While if it remains soft or leathery on gentle probing, it will be recorded as an active lesion.

STUDY PLAN

[figure not shown]

Figure: flow chart of the study plan

STATISTICAL ANALYSIS

The statistical software SPSS version 27.0 for Windows will be used for data analysis. The outcome variable is the number of colony forming units (CFU) of *streptococcus mutans and lactobacilli*, and the number of arrested caries lesions after 1 month in both the SDF and NSF groups. The collected data will be recorded and statistically evaluated.

The Chi square test will be used to compare the difference between the two groups regarding change caries lesion activity, the T-test or the Mann-Whitney U test will be used to analyze the differences between the microbiological samples, Wilcoxon signed rank will be used to assess the changes over time in bacterial counts. Regression analysis will be used to assess the potential confounders such as gender, social status, and dietary habits. The data will be graphically presented with suitable graphs. The level of statistical significance will be set at 5%.

ETHICAL CONSIDERATIONS IN SUBJECTS INVOLVING HUMAN SUBJECTS

1. This research protocol will be approved by the Research Ethics Committee of Alexandria University Faculty of Dentistry (IORG 0008839-IRB No. 0359-12/2021). prior to any research-related activities.
2. All research activities involving human subjects will abide by the Declaration of Helsinki³⁷ and other ethical guidelines adopted by the Research Ethics Committee of Alexandria University Faculty of Dentistry.
3. Benefits:
 - It will provide a caries arresting treatment for young children with multiple active carious lesions using minimally invasive atraumatic procedures.
 - It will allow overcoming the disadvantages of silver diamine fluoride including black staining of the teeth and any clothes it contacts, soft tissue injury, unpleasant taste for children.

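### The between-arm bacterial test is tied to no outcome form, scale or unit; name log10 CFU/ml at one month, one value per child, adjusted for the baseline count already collected

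*Combined protocol and SAP*

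**What the plan says.** The bacterial outcome appears in several forms.

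- Study Design, PICOT question: will the NSF children "show a greater percentage decrease in bacterial counts in the caries lesion" at one month?
- Specific aims: "To compare the change in" the two organisms' counts. Absolute or relative change is not stated.
- Study Outcome: "Treatment effect will be evaluated after one month by comparing" CFU of each organism, and caries activity.
- Statistical Analysis: "The outcome variable is the number of colony forming units (CFU) of" the two organisms, together with the number of arrested lesions.

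The between-arm analysis is one clause: "the T-test or the Mann-Whitney U test will be used to analyze the differences between the microbiological samples". The Wilcoxon signed rank test is assigned to change over time, which is a within-arm question. A regression is planned for potential confounders. Its list of examples is open-ended, does not mention the baseline count, and comes with no named outcome.

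A pre-treatment count is taken: a microbrush is "rubbed on the carious lesion for 4 seconds to collect the baseline microbiological sample". Every lesion "indicated for treatment with NSF or SDF will be treated and sampled for microbiological analysis". Eligibility requires "The presence of at least one active carious lesion on a primary tooth", and the Benefits paragraph expects children with multiple lesions. CFU/ml is the stated unit. No transformation is named, and there is no rule for counts of zero.

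**The concern.** One-month count and percentage decrease are different quantities. The first ignores where the child started; the second is fixed by the ratio of the one-month count to the baseline count. A plan that names both and ties its test to neither leaves the main comparison open until the data are in hand. The same applies to the scale, to the choice between the two tests and to the handling of several lesions per child.

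Two things are at stake. The answer may depend on a choice made after the data are seen. And the baseline count, which costs a sample per lesion, may go unused in the comparison between arms.

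**Working it through.** **1. The plan's sample size.** The 24 per group cannot be reproduced, because no effect size, SD, outcome or scale is given. It can be inverted. For a two-sample t-test with n=24 per arm, two-sided α=0.05 (sidedness is not stated) and 80% power, the standardised difference is d=0.826. The normal approximation gives (1.960+0.842)×√(2/24)=0.809. The step from 24 to 25 allows for 1/25=4% drop-out. I use d=0.826 on log10 counts below, which is a ratio of 10^(−0.826)=0.149 if the SD is 1 log10.

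**2. Why the form matters.** Let B and Y be log10 counts at baseline and one month, with equal SD and correlation r. Percentage decrease is 100×(1−10^(Y−B)), a monotone function of Y−B. A rank test on percentage decrease is therefore a rank test on log10 change. Relative to the one-month SD:

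- SD of change = √(2(1−r)): 1.414 at r=0, 1.265 at 0.2, 1.000 at 0.5, 0.775 at 0.7.
- Residual SD after baseline adjustment = √(1−r²): 1.000, 0.980, 0.866, 0.714.

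Change is noisier than the one-month count when r is below 0.5 and less noisy above it. Baseline adjustment is at least as precise as either at every r, apart from one degree of freedom.

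**3. Simulation.** Assumptions not in the documents: 24 children per arm, one lesion each, lognormal counts, log10 SD 0.5 or 1, difference 0.826 SD, r from 0 to 0.7. Power at two-sided 5%:

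| Analysis | r=0 | r=0.2 | r=0.5 | r=0.7 |
|---|---|---|---|---|
| Mann-Whitney, one-month count | 77–78% | 77–78% | 77–78% | 77–78% |
| Mann-Whitney, percentage decrease | 47–49% | 56–58% | 77–78% | 93–94% |
| t-test, log10 one-month count | 79–81% | 79–81% | 79–81% | 79–81% |
| ANCOVA, log10, on baseline | 78–80% | 80–81% | 89–90% | 97–98% |

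The two Mann-Whitney readings reach different conclusions at p<0.05 in about 35% of the same trials at r=0 and about 23% at r=0.7. Even at r=0.5, where their power is equal, they disagree in about a quarter. Against the log10 t-test, ANCOVA gains nothing at r of 0–0.2 and 9–18 points at r of 0.5–0.7.

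A t-test on untransformed counts has 54–56% power (SD 0.5) or 21–22% (SD 1).

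**4. Several lesions per child.** With 1–5 lesions per child and an intraclass correlation of 0.3–0.6 (assumed), Mann-Whitney with each lesion as a unit has a type I error of about 14–23% instead of 5%. ANCOVA on child means (r=0.5) has 5.1–5.4%.

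**5. Counts below the detection limit.** With half the limit substituted at both visits (SD 1, true ratio 0.149, r 0.2–0.7), ANCOVA estimates 0.16 with 94–95% coverage when 10% of all one-month counts are below the limit. At 20% it estimates 0.18 with about 93–94% coverage. At 46% of all counts (30% of the control arm) it estimates 0.28–0.29 with 60–73% coverage. The ratio is usable with few non-detects and misleading with many.

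**The case against.** **The texts can be partly reconciled.** CFU may be the measurement, and change or percentage decrease its summary. In the Statistical Analysis section the one-month wording follows the arrested lesions and may not qualify CFU. This is fair, and the conflict then rests mainly on the Study Outcome section against the PICOT question. But the test clause still names no quantity on any reading.

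**Mann-Whitney on percentage decrease, fixed in advance, would also end the ambiguity** and would keep the PICOT question. True, but its power is 47–58% at r of 0–0.2, and r is unknown. ANCOVA on log10 counts is within about a point of the best option shown, or ahead of it, at every r tried.

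**Stronger readings that the documents do not support:**

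- A reader might infer that the trial will run a t-test on raw counts and have 21–56% power. That is a worst case: the plan also offers Mann-Whitney, which a log transformation does not affect. In simulations in which a normality check selects the test (a rule not in the plan), Mann-Whitney was always chosen.
- A reader might infer that baseline adjustment is ruled out. The covariate list is open-ended, so it is unplanned, not excluded.
- A reader might infer that lesions will be analysed as independent. The plan does not say so; it gives no rule.
- A reader might take the 10 ml aliquot under Culture literally, against the 1 mL of saline the sample is carried in and the 1 in the Colony count equation, and conclude that the detection limit is uncertain by orders of magnitude. The same sentence specifies a micropipette, so the figure may be a unit slip or a misread symbol. It calls for a laboratory query, and a constant volume factor cancels in the NSF:SDF ratio.

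**Conclusion.** The concern holds as a gap in specification with an inexpensive remedy. The form, scale and unit of the between-arm bacterial analysis are not fixed, and the baseline count is not assigned to that analysis. Under the stated assumptions, two natural readings give different verdicts in roughly a quarter to a third of trials. The benefit of baseline adjustment depends on r: none at 0–0.2, 9–18 points of power at 0.5–0.7. The type I error of 14–23% applies only if lesions are treated as units.

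These sizes rest on lognormal counts, the back-solved difference of 0.826 SD, and assumed values of SD, r, lesion number and intraclass correlation. None of this shows that 24 per group is wrong: its inputs are not in the documents, so it is neither confirmed nor refuted.

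**What to change.** State the following for each organism.

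1. Endpoint: log10 CFU/ml at one month, one value per child, taken as the mean of the log10 counts over that child's treated lesions.
2. Between-arm analysis: ANCOVA with arm and the child's mean baseline log10 count. Report the back-transformed NSF:SDF ratio with its 95% CI.
3. Non-detects: one rule, for example half the detection limit, applied at both visits. Name a rank test on the one-month child values as the sensitivity analysis, and rely on it instead of the ratio if non-detects are common. Write that threshold as a number, judged on the pooled arms before unblinding; the check above gives no support for going beyond 20%.
4. Description only: percentage decrease and the within-arm Wilcoxon test. Align the PICOT question and the specific aim with the endpoint in item 1.

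Separately, ask the laboratory to reconcile the plated aliquot with the sample volume and the equation, so that the detection limit can be stated as a number.

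Cost: no added children, samples or visits. One degree of freedom is used, about 1 point of power if r=0. The treatment effect becomes a ratio of remaining counts instead of a difference in percentage decrease; from equal baselines, decreases of 99% and 90% correspond to a ratio of 0.01/0.10=0.10. The change does not settle whether one organism is primary; two tests at 5% remain, as now.

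### No species and no between-group measure is named as primary for the antibacterial comparison, the two bacterial counts share one 5% level with no testing order, and adjustment for the baseline count is not specified

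*Combined protocol and SAP*

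**What the plan says.** The Introduction states one null: "The null hypothesis of this study is that no statistically significant difference will be detected regarding the antibacterial effect of nanosilver fluoride" relative to SDF at one month. It names no species.

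The measure differs between sections:

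- **Specific aims, first aim:** "To compare the change in" the counts of both species.
- **Study Design, PICOT question:** asks whether NSF children will "show a greater percentage decrease in bacterial counts in the caries lesion (outcome; O"), again with no species.
- **Study Outcome:** lists CFU of both species and caries activity side by side, evaluated at one month.
- **Statistical Analysis:** gives the outcome variable as CFU of both species "and the number of arrested caries lesions after 1 month in both the SDF and NSF groups".

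For the analysis, the same section says that between groups "the T-test or the Mann-Whitney U test will be used to analyze the differences between the microbiological samples", that "Wilcoxon signed rank will be used to assess the changes over time in bacterial counts", and that "Regression analysis will be used to assess the potential confounders such as gender, social status, and dietary habits". On error control there is one sentence: "The level of statistical significance will be set at 5" per cent. No outcome is called primary, and there is no order of testing or multiplicity rule.

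The First visit section has a pre-treatment sample taken from every treated lesion, so a baseline count will exist for each child. No rule reduces several lesions to one value per child.

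**The concern.** The aims settle the domain (bacteria before lesion activity) but not the test that decides the question. Two things are left open.

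The first is which species carries the claim. Each has its own medium, incubation and count, and no combined measure is defined, so separate tests are the natural reading. With two tests at one 5% level and no order, a report could rest an antibacterial difference on whichever species reached significance.

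The second is what is compared. The wording for the between-group test fits either follow-up counts or changes. The signed rank test is paired, so it describes change within a group and cannot compare the groups. The aims and the PICOT question plainly intend baseline to be used, yet the between-group test does not adjust for it and the regression sentence does not name it. At stake are the error rate of the trial's main claim and some precision in a trial of 50 children.

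**Working it through.** **The plan's own figure.** The Sample size estimation section gives 24 per group at 80% power and 5%, raised to 25. It states no endpoint, effect, SD, specific test or sidedness, so 24 cannot be reproduced forward. Solved backwards with a two-sided two-sample t-test, 24 per group corresponds to a difference of 0.826 SD. This serves below only as the yardstick for a follow-up comparison.

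**Step 1. Error rate for two species.**

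Inputs: 5% per test (Statistical Analysis); two-sided tests (assumed, because the null is non-directional); correlation r between the two test statistics (assumed, because none is given); and the condition that a result on either species is enough.

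P(at least one) = 0.05 + 0.05 − P(both), where P(both) is the bivariate normal probability that both |z| exceed 1.96.

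| r | P(both) | P(at least one) |
|---|---|---|
| 0 | 0.0025 | 0.0975 |
| 0.5 | 0.0093 | 0.0907 |
| 0.7 | 0.0165 | 0.0835 |

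If both species were required, P(both) would apply and there would be no inflation.

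**Step 2. Detectable difference by choice of measure.**

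Inputs: 24 evaluable per group; two-sided 5%; 80% power; one value per child; normal log10 counts with SD 1 at both visits; baseline-to-follow-up correlation ρ (assumed, because none is given).

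SD of the quantity compared:

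- follow-up only: 1, with 46 df
- change: √(2(1 − ρ)), with 46 df
- ANCOVA: √(1 − ρ²), with 45 df

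The detectable difference is that SD times 0.826 (46 df) or 0.8265 (45 df), from the noncentral t. For ρ = 0.5 this gives:

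- change: √1 × 0.826 = 0.83
- ANCOVA: √0.75 × 0.8265 = 0.866 × 0.8265 = 0.72

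| ρ | Follow-up only | Change | ANCOVA | Gain over better simple option |
|---|---|---|---|---|
| 0.3 | 0.83 | 0.98 | 0.79 | 0.826 − 0.788 = 0.04 |
| 0.5 | 0.83 | 0.83 | 0.72 | 0.826 − 0.716 = 0.11 |
| 0.7 | 0.83 | 0.64 | 0.59 | 0.640 − 0.590 = 0.05 |

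At ρ = 0, follow-up only gives 0.826 and ANCOVA 0.827; at ρ = 0.1, 0.826 and 0.822. There is no material gain at these low correlations.

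Follow-up only is the better simple option below 0.5 and change is the better one above it. With ρ unknown, neither can be called safe in advance. ANCOVA is at least as good as both throughout, apart from the one degree of freedom lost near ρ = 0.

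**The case against.** Much of the opposing case stands and limits the point.

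- **The either-species rule is not written.** The plan states one null and one 5% level. Separate species tests are an inference, and nothing says that one success suffices. The rates in step 1 are therefore conditional.
- **Adding lesion arrest.** A reader might count three tests and quote 14.3% (independent), 12.5% (correlation 0.5) or 10.9% (0.7). The documents do not support that for the antibacterial claim: lesion activity is a separate specific aim with its own chi-square test and is no route to an antibacterial conclusion.
- **Choosing the measure after seeing the data.** In a null simulation, picking the better of follow-up and change gave about 9% false claims for one species and 16–18% for two. The documents leave the choice open but do not say it will be made on results.
- **Baseline left out, or the comparison biased.** Neither follows. The regression list is open-ended and its outcome and form are undefined, so baseline is not specified rather than excluded. Randomisation protects the unadjusted comparison from bias; the cost is precision.
- **The ANCOVA gain is modest and the model idealised.** The large contrast, 0.98 against 0.79 SD at ρ = 0.3, is with the poorer simple option. Zero counts could spoil normality or equal SDs, an effective agent could weaken ρ, and the Mann-Whitney alternative was not modelled.
- **The sample size.** It cannot be checked, but it is not shown to be wrong. The missing inputs are a reporting gap and no part of this point.

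**Conclusion.** The point holds in limited form. The lead aim is evident, but no species and no between-group measure is designated primary, and the two counts share one 5% level without an order. If either species would be accepted as showing a difference, the chance of a false claim is about 8–10% over assumed correlations of 0 to 0.7. If both were required, it does not exceed 5%. The plan does not say which rule applies, and that silence is the defect.

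Baseline adjustment is an improvement on offer, not the repair of a biased analysis. Under one value per child, normal log10 counts and equal SDs, it is worth about 0.04 to 0.11 SD over the better simple option at correlations of 0.3 to 0.7, and nothing near 0. Its main merit is that it removes the need to guess the correlation. The change should be made; the trial is not invalid without it.

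**What to change.** 1. Name one species' log10 CFU at 1 month as the primary outcome. The species is the sponsor's choice.
2. Compare groups by ANCOVA on the baseline log10 CFU. Use one value per child by a stated rule, for example the mean log10 count over treated lesions sampled at both visits, and state how zero counts are handled.
3. Report the back-transformed ratio of counts with its 95% CI. This also answers the PICOT question about percentage decrease.
4. Make the other species secondary, tested only if the primary is significant, or label it exploratory. Report lesion arrest as a separate secondary aim.

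Timing decides what this is worth. The choice must be made before anyone has seen follow-up results by group. The Blinding section leaves the investigator unblinded, so a blinded statistician is not enough. The title page carries 2021/2022 and an upload date of July 2023, and the schedule runs nine months, so results may already have been seen; the documents do not say. If they have, the choice must be labelled post hoc.

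Cost: no extra children, visits or samples, because the baseline count is already collected. The change is to text and analysis. The downside is that the two species lose co-equal status.
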